6.2. Secondary Objectives

The secondary objectives of this study are

[figure not shown]
- to estimate the PK parameters of LY3074828 following IV and SC administration in healthy Japanese and Caucasian subjects
- to explore the safety, tolerability, and PK of LY3074828 in Japanese subjects in relation to Caucasian subjects

7. Investigational Plan

7.1. Summary of Study Design

This is a single-site, subject- and investigator-blind, randomized, placebo-controlled, single-dose study to assess the safety, tolerability, and PK of LY3074828 in Japanese and Caucasian healthy subjects. Subjects will be randomized to LY3074828 or placebo within 1 of 6 cohorts, as shown in [Figure AMAD.2](#). Cohort 1 will consist of 10 subjects (6 Japanese and 4 Caucasian) who will be randomized so that 5 Japanese subjects and 3 Caucasian subjects will receive LY3074828 while 1 Japanese subject and 1 Caucasian subject will receive placebo. Cohorts 2 through 6 will consist of 8 subjects (4 Japanese and 4 Caucasian) who are randomized in a 3:1 ratio of LY3074828 to placebo. For each cohort, 3 Japanese subjects and 3 Caucasian subjects will receive LY3074828 while 1 Japanese subject and 1 Caucasian subject will receive placebo.

Single doses up to 600 mg IV have been studied and shown to be well tolerated, therefore all cohorts, with the exception of Cohort 5 and Cohort 6, may be dosed in parallel if the site is able to accommodate more than 1 cohort at a time. Cohort 5 will be dosed after confirming the safety and PK data from Cohort 1. Cohort 6 will be dosed last after confirming the safety and PK data from Cohort 5. Two additional Japanese subjects will be included in Cohort 1 to ensure that a sufficient number of Japanese subjects will have received LY3074828 at the time of the interim analysis. An interim analysis is planned based on Cohort 1 data through Day 15 (see [Section 11.3](#)) to support Japanese patients being included in the planned global Phase 2 study, Study I6T-MC-AMAC (AMAC).

Abbreviations: FU = follow up; IV = intravenous; SC = subcutaneous.

Figure AMAD.2. Study design for Protocol I6T-JE-AMAD.

Treatment:

Four IV dose levels and 1 SC dose level of LY3074828 will be assessed in Cohorts 1 through 6. The following treatments are planned:

- Cohort 1: a single dose of LY3074828 600 mg or placebo IV
- Cohort 2: a single dose of LY3074828 200 mg or placebo IV
- Cohort 3: a single dose of LY3074828 200 mg or placebo SC
- Cohort 4: a single dose of LY3074828 60 mg or placebo IV
- Cohort 5: a single dose of LY3074828 1200 mg or placebo IV
- Cohort 6: a single dose of LY3074828 2400 mg or placebo IV

Study Procedures:

Each subject will have a screening visit within 28 days prior to dosing, as shown in the Study Schedule ([Attachment 1](#)). AEs, including injection-site reactions, will be assessed on all clinical research unit (CRU) visit days and when spontaneously reported. Physical examination, vital

signs, ECGs, laboratory tests, PK and other sample collections will be performed at times specified in the Study Schedule ([Attachment 1](#)).

Subjects will report to the CRU on Day -2 and remain at the CRU until after the scheduled procedures have been completed on Day 2 ([Attachment 1](#)). After randomization, study drug will be administered by either IV or SC injection in the morning of Day 1 after an overnight fast.

Extension of admission to the CRU and additional outpatient visits may be required for safety reasons at the discretion of the investigator. If any safety findings warrant follow-up and/or preclude discharge from the study, further visits may be arranged as appropriate.

Sequential PK sampling and safety monitoring will occur through the end of study. There will be outpatient visits over approximately 12 weeks after study drug administration, including an End of Study visit (Day 85) that will occur approximately 12 weeks after the dose.

7.2. Discussion of Design and Control

This is a single-site, subject- and investigator-blind, randomized, placebo-controlled, single-dose study in healthy Japanese and Caucasian subjects. Healthy Caucasian subjects are included in this study to enable comparison between healthy Japanese and Caucasian subjects, as most of the subjects in Study AMAA were Caucasian patients with psoriasis. The number of subjects in Study AMAD is not sufficient for any formal ethnic comparison, but the safety, tolerability, and PK data will be assessed in both Japanese and Caucasian subjects and will be used to support the inclusion of Japanese subjects in future studies involving LY3074828. The study will be subject- and investigator-blind, with the subjects, investigators, and site staff (except for site pharmacy staff) unaware of actual treatment (LY3074828 or placebo), but aware of dose level assigned to the cohort. This design is being used to minimize bias in safety and tolerability assessments.

Dosing will begin with the 600 mg IV cohort because the timing of this cohort will determine the timing of the interim analysis and subsequent inclusion of Japanese subjects in the LY3074828 global studies. Single doses up to 600 mg have already been shown to be well tolerated in Study AMAA. The dose levels included in this single-dose study are within the range of doses studied previously, with the exception of the planned 1200 mg and 2400 mg IV dose cohort. Preliminary population PK analyses of interim data from Study AMAA indicate that body weight has no clinically significant impact on clearance or volume of distribution of LY3074828. Therefore, the AUC and maximum drug concentration (C_{max}) in Japanese subjects who may have lower body weight are expected to be similar to those of subjects in Study AMAA.

The follow-up period will be 12 weeks for all cohorts after dosing. This duration will allow ample time for assessment of the PK of LY3074828 (>5 half-lives) and for an initial assessment of ADAs.

8. Study Population

8.1. Criteria for Enrollment

Eligibility of subjects for study enrollment will be based on the results of a screening medical history, physical examination, vital signs, electrocardiogram (ECG), and clinical laboratory tests ([Attachment 1](#)).

A chest x-ray will be completed at screening unless one has been obtained within the past 12 months, and the x-ray and/or report are available for the investigator's review.

The nature of any conditions present at the time of the physical examination and any preexisting conditions will be documented.

Screening may occur up to 28 days prior to dosing. Subjects who are not enrolled within 28 days of screening may be subjected to an additional medical assessment and/or clinical measurements to confirm their eligibility.

Individuals who do not meet the criteria for participation in this study (screen failure) may not be rescreened. However, if individuals have met the criteria for participation in this study but their screening assessments were collected outside of the 28-day screening window, those assessments may be repeated.

Prospective approval of protocol deviations to recruitment and enrollment criteria, also known as protocol waivers or exemptions, are not permitted.

8.1.1. Inclusion Criteria

Subjects are eligible for enrollment in the study only if they meet all of the following criteria:

[1] are overtly healthy males or females, as determined by medical history and physical examination

[1a] male subjects:

will be sterile (including vasectomy) or agree to use a reliable method of birth control and will not donate sperm during the study and for 3 months following administration of the study drug

[1b] female subjects:

are women of childbearing potential who test negative for pregnancy before receiving study treatment based on serum pregnancy test and agree to use a reliable method of birth control (for example: barrier methods such as condom, sponge, or diaphragm combined with spermicide in foam, gel, or cream; hormonal contraception [oral, intramuscular, implant, or transdermal], which includes Depo-Provera, Evra, and NuvaRing; intrauterine device; or complete abstinence from sexual intercourse with men) during the study and for 3 months following administration of the study drug

or

are women not of childbearing potential due to surgical sterilization (at least 6 weeks after bilateral oophorectomy and/or hysterectomy or at least 6 weeks after tubal ligation) confirmed by medical history, or postmenopausal, defined as either:

1) spontaneous amenorrhea for at least 12 months, not induced by a medical condition or medications

or

2) spontaneous amenorrhea for 6 to 12 months with a follicle-stimulating hormone level greater than 40 mIU/mL at screening

- [2] are first-generation Japanese or are Caucasian. **CCI**

- [3] are 20 years to 64 years, inclusive, at the time of initial screening
- [4] have a body mass index (BMI) of 18.0 kg/m² to 32.0 kg/m², inclusive, at screening
- [5] have a body weight of 40.0 kg or higher for Cohorts 1 to 4 and 48.0 kg or higher for Cohort 5 and Cohort 6
- [6] have clinical laboratory test results within normal reference range for the population or investigator site, or results with acceptable deviations that are judged to be not clinically significant by the investigator
- [7] have venous access sufficient to allow for blood sampling and administration of IP as per the protocol
- [8] are reliable and willing to make themselves available for the duration of the study and are willing to follow study procedures
- [9] have given written informed consent approved by Lilly and the ethical review board (ERB) governing the site

8.1.2. Exclusion Criteria

Subjects will be excluded from study enrollment if they meet any of the following criteria:

- [10] are investigator site personnel directly affiliated with this study and their immediate families. Immediate family is defined as a spouse, parent, child, or sibling, whether biological or legally adopted.
- [11] are Lilly employees or employees of the third-party organizations (TPOs) involved with the study
- [12] are currently enrolled in a clinical trial involving an IP or off-label use of a drug or device or are concurrently enrolled in any other type of medical research judged not to be scientifically or medically compatible with this study

- [13] have participated, within the last 30 days, in a clinical trial involving an IP. If the previous IP has a long half-life, 3 months or 5 half-lives (whichever is longer) should have passed.
- [14] are persons who have previously completed or withdrawn from this study or any other study investigating LY3074828 or any other anti-IL-23 antibody and have previously received the IP
- [15] have known allergies to LY3074828, related compounds including humanized monoclonal antibodies, or any components of the formulation or history of significant atopy
- [16] have clinically significant multiple or severe drug allergies, intolerance to topical corticosteroids, or severe posttreatment hypersensitivity reactions (including but not limited to erythema multiforme major, linear immunoglobulin A (IgA) dermatosis, toxic epidermal necrolysis, or exfoliative dermatitis)
- [17] have an abnormality in the 12-lead ECG that, in the opinion of the investigator, increases the risks associated with participating in the study
- [18] have an abnormal blood pressure as determined by the investigator
- [19] have a significant history of or current cardiovascular, respiratory, hepatic, renal, gastrointestinal, endocrine, hematological, or neurological disorders capable of significantly altering the absorption, metabolism, or elimination of drugs; of constituting a risk when taking the study medication; or of interfering with the interpretation of data
- [20] have known or ongoing psychiatric disorders
- [21] regularly use known drugs of abuse and/or show positive findings on urinary drug screening
- [22] show evidence of human immunodeficiency virus (HIV) infection and/or positive human HIV antibodies at screening
- [23] show evidence of hepatitis C and/or positive hepatitis C antibody at screening
- [24] show evidence of hepatitis B and/or positive hepatitis B surface antigen or positive hepatitis B core antibody (HBcAb+) at screening
- [25] are women who are lactating
- [26] have used or intend to use over-the-counter or prescription medication, including herbal medications, within 14 days prior to dosing (stable doses of oral contraceptive, hormone replacement therapy, or vitamins at usual doses may be allowed as per judgment of the investigator)
- [27] have donated blood of more than 500 mL within the last month

- [28] are subjects who have an average weekly alcohol intake that exceeds 21 units per week for males and 14 units per week for females or who are unwilling to abide by the alcohol restrictions described in Section 9.5
- [29] are subjects whose tobacco consumption is more than 10 cigarettes per day or the equivalent or subjects who are not willing to refrain from smoking for approximately 2 hours prior to each ECG and vital-sign measurement during the study or who are unwilling to abide by the CRU smoking guidelines (Section 9.5)
- [30] have had symptomatic herpes zoster within 3 months of screening
- [31] show evidence of active or latent tuberculosis (TB), as documented by medical history and examination, chest x-rays (posterior anterior and lateral), and TB testing: to qualify for the study, subject must have either a negative tuberculin skin test (TST; defined as a skin induration <5 mm at 48 hours to 72 hours, regardless of BCG [Bacillus Calmette-Guerin] or other vaccination history), or a negative (not indeterminate) QuantiFERON®-TB Gold test. The choice to perform a TST or a QuantiFERON-TB Gold test will be made by the investigator according to local licensing and standard of care.
- [32] have received live vaccine(s) within 1 month of screening or intend to during the study
- [33] are immunocompromised
- [34] have received treatment with biologic agents (such as monoclonal antibodies, including marketed drugs) within 3 months or 5 half-lives (whichever is longer) prior to dosing
- [35] have had lymphoma, leukemia, or any malignancy within the past 5 years except for basal cell or squamous epithelial carcinomas of the skin that have been resected with no evidence of metastatic disease for 3 years
- [36] have had breast cancer within the past 10 years
- [37] in the opinion of the investigator or sponsor are unsuitable for inclusion in the study for any reason

8.1.3. Rationale for Exclusion of Certain Study Candidates

Criteria [10] and [11] prevent conflict of interest in study participants. Criteria [12] through [37] exclude medical conditions, medication intolerance, and concomitant medication use that may constitute a risk for the subject and/or may confound the assessment of study endpoints.

8.2. Discontinuation

The reason for and date of discontinuation will be collected for all subjects. All randomized subjects who discontinue after receiving study drug will have procedures performed as shown in the Study Schedule (Attachment 1).

8.2.1. Discontinuation of Subjects

8.2.1.1. Subjects Inadvertently Enrolled

The criteria for enrollment must be followed explicitly. If the investigator site identifies a subject who did not meet enrollment criteria and who was inadvertently enrolled, the sponsor must be notified. If the sponsor identifies a subject who did not meet enrollment criteria and who was inadvertently enrolled, the investigator site will be notified. A discussion must occur between the Lilly clinical pharmacologist or clinical research physician and the investigator to determine whether the subject may continue in the study without IP. The subject may not continue in the study if the Lilly clinical pharmacologist or clinical research physician does not agree with the investigator's determination it is medically appropriate for the subject to continue. The investigator must obtain documented approval from Lilly clinical pharmacologist or clinical research physician to allow the inadvertently enrolled subject to continue in the study.

8.2.1.2. Discontinuations from Investigational Product or from the Study

Subjects will be discontinued from the IP and/or from the study in the following circumstances:

- enrollment in any other clinical trial involving an IP or enrollment in any other type of medical research judged not to be scientifically or medically compatible with this study
- investigator decision
 - the investigator decides that the subject should be discontinued from the study
- subject decision
 - the subject requests to be discontinued from the study
- sponsor decision
 - Lilly stops the study or stops the subject's participation in the study for medical, safety, regulatory, or other reasons consistent with applicable laws, regulations, and good clinical practice (GCP)
- adverse event
 - if a clinically significant event (CSE) occurs during the IV infusion or SC injection, the IP is to be discontinued and appropriate measures taken. Lilly or its designee should be alerted immediately. A CSE will be defined as a moderate to severe AE, abnormal clinical sign, or clinical laboratory finding that may pose a risk to the well-being of the subject. Refer to Safety Evaluations (Section 10.5).
 - a clinically significant systemic hypersensitivity reaction occurs following administration of the IP (for example, drug-related symptomatic bronchospasm, allergy-related edema/angioedema, or hypotension) that requires parenteral medication, does not respond to symptomatic medication, or results in clinical sequelae or an anaphylactic reaction

A dose group may be discontinued from the IP if the following are met:

2 or more subjects/cohort develop AEs that are severe, unless there is an obvious explanation other than IP or study procedures for the event(s)

OR

if greater than 40% of subjects in a cohort experience moderate treatment-related AEs that impair normal activities

OR

after the introduction of premedication in accordance with the protocol, 2 or more subjects develop (according to Common Terminology Criteria for Adverse Events [CTCAE], version 4.0) \geq Grade 2 acute AEs related to the infusion, during or within 2 hours of completing the infusion, that do not resolve with a reduced infusion rate and/or supportive care

Following the investigator's determination that CSE criteria have been met and the investigator's judgment of relatedness to the IP is documented, a decision will be made between the investigator and Lilly or its designee regarding subject discontinuation.

The nature of any conditions, clinical signs or symptoms, or abnormal laboratory values present at the time of discontinuation and any applicable follow-up procedures will be documented.

Refer to the Study Schedule ([Attachment 1](#)) for data collected at the time of discontinuation.

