
Study Design: Study I6T-JE-AMAD is a single-site, subject- and investigator-blind, randomized, placebo-controlled, single-dose study to assess the safety, tolerability, and PK of LY3074828 in Japanese and Caucasian healthy subjects. The study will consist of 6 planned dose cohorts: 5 IV cohorts (60 mg, 200 mg, 600 mg, 1200 mg, and 2400 mg) and 1 SC cohort (200 mg). Subjects in each cohort will be randomized to receive LY3074828 or placebo. Subjects will be inpatient in the clinical research unit (CRU) for treatment administration and will then be discharged and followed as outpatients for 12 weeks after treatment administration.
	

Diagnosis and Main Criteria for Inclusion and Exclusion: This study will enroll healthy male and female subjects who are 20 years to 64 years, inclusive, with a body mass index of 18.0 kg/m² to 32.0 kg/m², inclusive, at screening. Japanese subjects must be first-generation Japanese, defined as the subject, the subject's biological parents, and the subject's biological grandparents are all of exclusive Japanese descent and were born in Japan.
	

Investigational Product, Dosage, and Mode of Administration: A single dose of LY3074828 will be administered IV at the planned dose levels of 60 mg, 200 mg, 600 mg, 1200 mg, and 2400 mg. A single dose of LY3074828 will be administered SC at a planned dose of 200 mg.
	

Comparator, Dose, and Mode of Administration: A single dose of placebo (sterile normal saline [0.9% sodium chloride]) will be given IV or SC, as per cohort.
	

Planned Duration of Treatment: LY3074828 or placebo will be given as a single dose.
	

Criteria for Evaluation:
 
Safety: Adverse events (AEs), serious adverse events, physical examinations, vital signs, electrocardiograms (ECGs), and clinical laboratory evaluations including immunogenicity.
 
Bioanalytical: Serum for the measurement of LY3074828 concentrations will be collected at select visits.
 
Pharmacokinetic: The primary parameters for analysis will be maximum drug concentration (C_{max}) and area under the concentration versus time curve (AUC) of LY3074828. Other noncompartmental parameters, such as half-life, clearance, and volume of distribution (apparent clearance and apparent volume of distribution for SC administration) may be reported.
	

Evaluation Methods:

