Therefore, this study planned to evaluate the safety, tolerability, and PK of a 1200-mg IV dose of LY3074828. The 1200-mg IV dose cohort (Cohort 5) was dosed after safety, tolerability, and PK data were confirmed from the 600-mg dose cohort (Cohort 1). Other dose levels were dosed concurrently in this study because these doses have already been shown to be well tolerated in Study AMAA. Evaluation of 1200-mg IV dose cohort (Cohort 5) provided safety and PK data to support the use of a higher dose level in Study AMAC and Study AMAG.

In addition to the above evaluation, this study is amended to add the evaluation of safety, tolerability, and PK of a 2400-mg IV dose of LY3074828, since there is a possibility to evaluate a higher dose level up to 2400 mg IV in later clinical development. The proposed dose of 2400-mg IV infusion has a sufficient margin of safety in terms of dose. Moreover, the clinical safety profile of LY3074828 available to date supports 2400-mg IV administration in this study. Single doses of up to 1200 mg IV were evaluated in healthy subjects from Study AMAD and no dose-related safety or tolerability issues were observed. Evaluation of the safety data available to date in the ongoing Study AMAC and Study AMAG that are evaluating higher and more frequent dose regimens of up to 1000 mg IV Q4W for up to 52 weeks has not revealed any differences in the safety profile. The PK profile of this drug was found to be approximately linear up to 1200-mg IV administration. Since the 2400-mg IV dose is only 2-fold of 1200 mg, it

is unlikely that an unexpected PK profile will be observed after administration of a 2400-mg IV dose. Therefore, evaluation of this additional higher dose cohort (2400 mg) will provide safety and PK data to support the use of a higher dose level beyond 1200 mg during the clinical development of this compound.

Table AMAD.2. Margin of Safety for Intravenous Administration of 2400 mg LY3074828 Based on Administered Dose and Predicted Exposure

	Dose (mg/kg)	Dose Multiple ^a	AUC _{0-672h,ss} (μ g•h/mL)	Margin of Safety ^b
Human highest dose (2400 mg)^c	36.9 (IV)		110000	
Monkey NOAEL^d 6-month study	100 (SC)	2.7	85800 ^e	0.78
Monkey NOAEL^f 4-week study	100 (IV)	2.7	204200 ^g	1.9

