9.4.1. Dose Escalation Method

Safety data, in particular AEs, SAEs, and adverse laboratory abnormalities, will be independently assessed by the investigator, and will be considered related to the IP unless there is clear evidence that the event is not related. The assessment of AE relatedness is detailed in Section 10.5.1. PK data included in the interim analysis will also be assessed.

After review of the data, an agreement on the appropriate dose escalation will be made by the investigator and sponsor for Cohort 6. None of the following scenarios occurred at 1200-mg LY3074828:

2 or more subjects develop AEs that are severe, unless there is an obvious explanation other than IP or study procedures for the event(s)

OR

if greater than 40% of subjects experience moderate treatment-related AEs that impair normal activities

OR

after the introduction of premedication in accordance with the protocol, 2 or more subjects develop (according to Common Terminology Criteria for Adverse Events [CTCAE]) ≥Grade 2 acute AEs related to the infusion, during or within 2 hours of completing the infusion, that do not resolve with a reduced infusion rate and/or supportive care.

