10.5.1. Adverse Events

Lilly has standards for reporting AEs that are to be followed regardless of applicable regulatory requirements that may be less stringent.

Cases of pregnancy that occur during maternal or paternal exposures to the IP should be reported. Data on fetal outcome and breast-feeding are collected for regulatory reporting and drug safety evaluation.

After the informed consent form (ICF) is signed, site personnel will record any change in the condition(s) and the occurrence and nature of any AEs. All AEs related to protocol procedures are reported to Lilly or designee.

Any clinically significant findings from ECGs, laboratory values, vital sign measurements, and other procedures should be reported as an AE to Lilly or its designee.

In addition, all AEs occurring after the subject receives the first dose of the IP must be reported to Lilly or its designee via CRF.

Investigators will be instructed to report to Lilly or its designee their assessment of the potential relatedness of each AE to protocol procedure, IP, and/or drug delivery system via the CRF.

The investigator decides whether he or she interprets the observed AEs as either related to disease, study medication, study procedure, or other concomitant treatment or pathologies. To assess the relationship of the AE to the IP, the following terminologies are defined:

- **Related:** A direct cause and effect relationship between the study treatment and the AE is likely.
- **Possibly related:** A cause and effect relationship between the study treatment and the AE has not been demonstrated at this time and is not probable but is also not impossible.
- **Unrelated:** Without question, the AE is definitely not associated with the study treatment.

As per Lilly's standard operating procedures all "related" and "possibly related" AEs and SAEs will be defined as related to the IP.

If a subject's dosage is reduced or treatment is discontinued as a result of an AE, study site personnel must clearly report to Lilly or its designee via CRF the circumstances and data leading to any such dosage reduction or discontinuation of treatment.

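### Protocol 8.2.1.2: the 40% dose-group criterion omits severe events from its count and includes placebo subjects in its denominator, two separate minor defects that now matter only for Cohort 6

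*Protocol*

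**What the plan says.** Protocol 8.2.1.2 lists three alternative conditions under which a dose group *may* be discontinued. The second is met "if greater than 40% of subjects in a cohort experience moderate treatment-related AEs that impair normal activities". The first concerns severe AEs in two or more subjects per cohort, unless something other than the IP or study procedures obviously explains them. The third covers acute infusion-related events and applies only once premedication has been introduced.

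Protocol 7.1 sets Cohorts 2 to 6 at 8 subjects each: "For each cohort, 3 Japanese subjects and 3 Caucasian subjects will receive LY3074828 while 1 Japanese subject and 1 Caucasian subject will receive placebo". So *cohort* covers both arms. For timing, 7.1 says "Cohort 6 will be dosed last after confirming the safety and PK data from Cohort 5". Protocol 9.3 reports the 1200 mg cohort as already dosed and adds, "Other dose levels were dosed concurrently in this study". Cohort 6 is therefore the only cohort on which the criterion can still act.

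Three further provisions bear on the count:
- Under Protocol 10.5.1, related and possibly related "AEs and SAEs will be defined as related to the IP", and the Protocol's definition of IP includes placebo. An event in a placebo subject can therefore be counted.
- Dosing is single: "LY3074828 or placebo will be given as a single dose" (Protocol synopsis).
- The sponsor is unblinded (Protocol 9.6) and monitors safety throughout (Protocol 10.5.4).

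**The concern.** A tolerability criterion should not become harder to meet when an event is worse. Read literally, this one does: an event graded severe instead of moderate leaves the 40% count and enters a different count that needs two. Elsewhere in 8.2.1.2 the definition of a clinically significant event spans moderate to severe, so wider wording was at hand.

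Separately, tolerability of a dose is best judged in those who received it. With 2 of 8 subjects on placebo, a 40% threshold on the cohort requires 4 of 6 recipients (67%) when no placebo event is counted. Cohort 6 receives 2400 mg, twice the highest dose given before in this study.

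What is at stake is limited to Cohort 6 subjects not yet dosed when a criterion is met. No later escalation in this study depends on it.

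**Working it through.** **Inputs.** Cohort 6 has 8 subjects, 6 on LY3074828 and 2 on placebo (7.1). The threshold is strictly more than 40%, and the severe criterion needs 2 or more (8.2.1.2). The plan's own total reproduces: 10 + 5 × 8 = 50. The plan gives no subject count for the 40% criterion.

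**Defect 1, severity.** Let m be the subjects whose worst related event is moderate and s those whose worst is severe, with no premedication-related trigger. On the planned 8:
- current text: met if m ≥ 4 or s ≥ 2;
- *at least moderate*: met if m + s ≥ 4 or s ≥ 2.

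The two differ only when s ≤ 1, m ≤ 3 and m + s ≥ 4, which means m = 3 and s = 1. There the current count is 3/8 = 37.5% with one severe event, so neither criterion is met. The count at moderate or worse is 4/8 = 50%.

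**Defect 2, denominator.** The smallest count above 40% of N is floor(0.4N) + 1.

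| Denominator | Count needed | Three events give |
|---|---|---|
| 6 (LY3074828 only) | 3 | 3/6 = 50% |
| 7 | 3 | 3/7 = 42.9% |
| 8 (whole cohort) | 4 | 3/8 = 37.5% |

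One counted placebo event closes the gap: (3 + 1)/8 = 50%. The text does not say whether the denominator is the planned cohort or those dosed so far. On the second reading the counts needed for 1 to 8 dosed are 1, 1, 2, 2, 3, 3, 3, 4.

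**Size of an added trigger of 3 or more LY3074828 recipients.** The documents give no event rate at 2400 mg and no dosing interval within Cohort 6. Assumed: event rate p = 0.2 to 0.6 on LY3074828 and q = 0 to 0.2 on placebo, random dosing order, planned denominator of 8. Enumerating all C(8,2) = 28 orders gives the mean number of extra LY3074828 recipients left undosed when the trigger is added to the current rule (severity wording not included):

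| Dosing | Extra spared |
|---|---|
| all 8 before events are known | 0 |
| 4 at a time | 0.02 to 0.52 |
| 2 at a time | 0.05 to 0.78 |
| 1 at a time, each outcome known first | 0.06 to 0.91 |

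Protocol 5.1 suggests lower rates. In Study AMAA, 38 subjects received LY3074828 and none had a LY3074828 TEAE of Grade 2 or higher. If Grade 2 is taken as moderate, the one-sided 95% upper bound is 1 − 0.05^(1/38) = 7.6%. At p = 0.05 to 0.08 the same enumeration gives at most 0.007. Those doses went only to 600 mg IV, so higher rates at 2400 mg are not excluded.

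On the dosed-so-far reading the added trigger spares nobody: three events already exceed 40% until 7 are dosed, and at 8 no one is left.

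**Triggering in a complete cohort at p = 0.2.** Let X be the LY3074828 recipients with an event. The current rule is met with probability 0.017 (q = 0) to 0.056 (q = 0.2). With the trigger added, the probability is P(X ≥ 3) + P(X = 2) × q². That is 0.099 at q = 0, and 0.099 + 0.246 × 0.04 = 0.109 at q = 0.2.

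**The case against.** The strongest case for leaving the text alone is that counting the whole cohort is a legitimate choice in an investigator-blind study, because the investigator can apply it without treatment codes. The rule is permissive. Investigator and sponsor decisions and the stop for clinically significant events during administration operate independently, and the unblinded sponsor can act at any time. All of this stands, and it is why the point is minor. It does not explain why a severe event should leave the count.

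A reader might infer three stronger things that the documents do not support.
- *That the moderate-only wording causes the 3/8 result.* It does not. That result comes from the denominator alone.
- *That the denominator should simply be replaced by the 6 planned LY3074828 recipients.* This helps only on the planned-8 reading. If the count is of those dosed so far, the current text can be met earlier, for example at 2 of 4. Over the assumed rates, replacement would then spare about 0.3 to 2.6 fewer recipients when dosing is in blocks of four, two or one.
- *That the step to 2400 mg rested on a diluted count.* Protocol 9.4.1 states, "None of the following scenarios occurred at 1200-mg LY3074828". It is a record of a completed determination, and its wording already points to LY3074828 recipients.

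**Conclusion.** Both defects hold, and both are minor. The severity gap changes the answer in one pattern on the planned 8: three moderate plus one severe. The denominator gap arises when exactly 3 of 6 LY3074828 recipients and no placebo subject have a counted event. It rests on the planned-8 reading, which the text neither states nor excludes.

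The protection at stake from the denominator averages less than one LY3074828 recipient in every scenario tried. It is zero if all are dosed before events are known, and close to zero at rates compatible with Study AMAA. These figures depend on assumed event rates and dosing order. The documents do not support a reading that Cohort 6 is left unprotected.

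**What to change.** In Protocol 8.2.1.2:
1. Change *moderate* to *at least moderate* in the 40% criterion.
2. Keep the whole-cohort criterion and add an alternative: *or 3 or more LY3074828 recipients in Cohort 6 have treatment-related AEs of at least moderate severity that impair normal activities*. The unblinded sponsor makes this count and tells the investigator only whether it is met. As an absolute number, it needs no decision on planned versus dosed denominators.

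Leave Protocol 9.4.1 unchanged.

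The first change costs essentially nothing. The second needs no new unblinding of the sponsor but has two costs. Triggering is more frequent even at a low true rate: at 20% on LY3074828, 0.10 to 0.11 of complete cohorts against 0.02 to 0.06 now. And if the cohort is paused when only the sponsor-counted trigger is met, the investigator could infer that all three affected subjects received LY3074828.
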